#### **Introduction:-**

Melatonin (N-acetyl-5-methoxy-tryptamine) is an indoleamine synthesized and secreted by the pineal gland and other organs, such as the retina, bone marrow, and intestines in a circadian pattern. Extrapineal sites contribute poorly, or only upon specific stimuli to circulating melatonin (Hardeland et al., 2006). Melatonin influences numerous physiological actions that may be mediated by the binding of the indoleamine to membrane receptors in all tissues (Girgert et al., 2009). Because of its lipophilic properties, melatonin passes through cell membranes to gain access to subcellular organelles (Hevia et al., 2008), being capable to bind to some cytosolic proteins like kinase-C (Macías et al., 2003). Currently, melatonin is not considered a hormone in the classical sense of the term, because it is synthesized in several organs and does not exert effects on a specific target (Tan et al., 2003), but it is rather a powerful cell protector against molecular damage. For the synthesis of melatonin, the pineal cells take up tryptophan from the blood and, through hydroxylation and a decarboxylation process, turn it into serotonin. Serotonin is then converted into N-acetylserotonin through N-acetyltransferase and subsequently methylated to the final form of melatonin by the enzyme hydroxy indole-O-methyltransferase (Reiter, 1991) (Figure 1). In healthy individuals, the maximum secretion of melatonin occurs between midnight and 2 a.m., then it decreases to a minimum during the day (Simonneaux and Ribelayga, **2003)**. Melatonin has numerous physiological functions in different parts of the body, such as the control of circadian rhythms (McArthur et al., 1997), regulation of body temperature(Dollins et al., 1994), and activation of the immune system(Guerrero and Reiter, 2002). In the oral cavity, melatonin has been recognized as an important substance with paracrine effects on nearby cells(Tresguerres et al., 2002), it also acts as an antioxidant and an antiinflammatory and plays an important role in bone formation and in the reduction of bone resorption (Peyrot et al., 2008, Hardeland et al., 2009).

[figure not shown]

Figure 1. Melatonin synthesis and representation of its molecule (Reiter, 1991)

Osseointegration defined as a direct connection between living bone tissues and a titanium implant without any connective tissues. Osteoblasts are bone formative cells, and osteoclasts are bone resorptive cells. When these cells work together physiologically, the formation and resorption processes of bone tissue is known as bone remodelling. The remodeling of bone tissues is regulated by the action of systemic hormones (estradiol, parathyroid, growth, and melatonin) and by the bone marrow and osteoid matrix-derived growth factors(**Tresguerres et al., 2012, Wulandari**).Insufficient bone quality and quantity can be seen frequently in elderly populations with atrophic and osteoporotic bones, and this situation stems from increased osteoclastic activity due to a reduction in osteoblastogenesis. In addition, local free radical concentrations in all body cells, including osteoblasts, can reduce osteoblastic activity in aged patients. This process could lead to a reduction in bone regeneration capacity(**Cao et al., 2005**). Melatonin can also suppress osteoclastogenesis, and therefore inhibit bone tissue

resorption(Cutando et al., 2008, Witt-Enderby et al., 2006). In addition to this, in vitro research has reported that melatonin can increase osteoblast proliferation and differentiation (López-Martínez et al., 2012, Muñoz et al., 2012). So was proposed that the local application of melatonin during surgical implant placement procedures would be an effective treatment technique for dental implant osseointegration (Dundar et al., 2016). Worthy osseointegration is a prerequisite for dental implants. Optimal osseointegration depends on the formation of new bone around implants, which may be stimulated by the application of biomimetic agents (Ramazanoglu et al., 2011). Considering the bone metabolism, melatonin acts directly on the osteoclast, a multinucleated cell, which resorbs the extracellular matrix through various mechanisms, including the production of free radicals (Roth et al., 1999). Moreover, in pre-osteoblast cultures from rats, melatonin, in a dose-dependent manner, promoted the development of bone sialoprotein and other protein bone markers, including alkaline phosphatase, osteopontin, and osteocalcin, and speeds up their period of differentiation into osteoblasts from the normal rate, which is 21 days, to 12 days, this reaction is mediated by the membrane receptors for the indole(Roth et al., 1999). Also, melatonin, may interfere with the function of the osteoclast and thereby inhibit bone resorption(Cardinali et al., 2003). (Cutando et al., 2008) conducted an experimental study using melatonin with dental implants in dogs. Two weeks after implant insertion, melatonin significantly increased all parameters of osteointegration. It has been observed that melatonin, increases bone mass by suppressing resorption through down-regulation of the RANKLmediated osteoclast formation and activation (Cutando et al., 2007). These data point towards an osteogenic effect of melatonin that may be of clinical importance, as it could be used as a therapeutic agent in situations in which bone formation would be advantageous, such as in the treatment of fractures or of osteoporosis (Cardinali et al., 2003).

#### **Toxicology of Melatonin:-**

The physiological functions of the pineal hormone melatonin are extremely diverse. The functions include direct and indirect modulations of anti-oxidative defense, blood pressure, body temperature, cortisol rhythm, reproduction and immune function (Claustrat and Leston, 2015). Correspondingly, exogenous melatonin has been investigated as a treatment for a number of medical and surgical diseases, demonstrating encouraging results (Andersen et al., 2014, Gitto et al., 2011). In the USA, melatonin is available as an over-the-counter nonprescription drug. In most European countries, however, melatonin remains a prescription drug (Circadin) and has only been approved as a treatment for primary insomnia in people over 55 years of age. However, a recent Norwegian register study documented a 3- to 5-times increase in off-label use among children and adolescents in the time period 2004 to 2012 (Hartz et al., 2015). Melatonin is generally considered safe (Yousaf et al., 2010), but the increasing clinical use with potentially increasing doses necessitates further investigations of the risks of both mild and serious adverse effects. In experimental animal studies, exogenously administered melatonin has been given in doses up to 800 mg/kg without any acute toxic effects (Barchas et al., 1967). A number of studies in preterm infants have investigated the anti-oxidative/anti-inflammatory and clinical effects of exogenous melatonin in different conditions, such as pain during tracheal intubation (10 mg/kg x 10 doses, randomized)(Gitto et al., 2012), asphyxia (10 mg x 8 doses, randomized) (Fulia et al., 2001), respiratory distress (10 mg/kg x 10 doses, randomized)(Gitto et al., 2004b). Despite repeated high doses of intravenous melatonin, no signs of adverse effects were observed (Gitto et al., 2004c, Gitto et al., 2004a). Oral melatonin in doses of 0.5-10 mg was administered daily from 10 days to 12 weeks to improve sleep quality (Wright et al., 2011, Cortesi et al., 2012). The studies performed detailed registration of possible adverse effects, demonstrating a number of mild adverse effects, such as agitation, dizziness, headache, nausea, and sleepiness (Wasdell et al., 2008, Jain et al., 2015). Another study was to assess the toxicology of melatonin (10 mg), administered for 28 days to 40 volunteers randomly assigned to groups receiving either melatonin (N\_30) or placebo (N\_10) in a double-blind fashion, according to

the parameters analyzed, there is no toxicological effect that might compromise the use of melatonin at a dose of 10 mg for the period of time utilized in this study**(Seabra et al., 2000)**. A randomized, double-blind, placebo-controlled study including 54 female patients undergoing breast cancer surgery were given 6 mg of oral melatonin or placebo to improve depressive symptoms and anxiety during a three month investigational period **(Hansen et al., 2014)**. Finally, a randomized, double-blind, placebo-controlled study was conducted in elderly patients suffering from Alzheimer's disease who were administered 2 mg of melatonin or placebo for a 24-week period **(Wade et al., 2014)**. A substantial number of both animal and human studies document that short-term use of melatonin is safe, even in extreme doses. No studies indicate that exogenous melatonin possesses any serious adverse effects. Also, randomized clinical studies indicate that long-term administration only induces mild adverse effects comparable to placebo treatment. **(Andersen et al., 2016)**.

#### **Periotest M device:-**

Periotest device was developed to measure the damping characteristics of natural teeth and has been used to evaluate implant (Cehreli et al., 2009). It was developed by Schulte in 1983 to quantify TM (Shulte et al., 1983), and then utilized by Teerlinck et al. (1991), to measure implant stability and to overcome destructive methods in measuring the implant stability like histologic analysis, tensional test, push-out/pull-out test and removal torque analysis. The (Classic/Wired) Periotest device has been the subject of several studies with generally favorable results. These results showed that the Periotest device generally demonstrated a high degree of repeatability and reliability. A wireless version of the Periotest (Periotest "M") has been introduced to the profession. According to information provided by the electronic page of the Periotest M /wireless device manufacturer (Medizintechnik Gulden, Modautal, Germany), Periotest M is simpler to perform an objective evaluation of an implant's stability compared to classic Periotest. In Periotest M wireless design, the user can benefit from maximum freedom of movement. The device can be used for taking measurements on a wide variety of implants, without the need for any special accessories, such as a smart peg (Pang et al., 2014). The Periotest has an

important advantage against the others like the Osstell device: it can be applied directly to the implant superstructure **(Geckili et al., 2009)**.

The limitations of Periotest are the inability of the instrument to measure the mesiodistal mobility, the possible effect of position and angle of the rods on the measured value **(Satwalekar et al., 2015)**. The readings of PTV are from (-8 to +50) according to information provided by the device manufacturer (Medizintechnik Gulden, Modautal, Germany) **(Pang et al., 2014)**, **(Table 1)**. These readings are displayed digitally on a monitor as (PTVs), **(Aparicio et al., 2006)**.

(Table 1): Interpretation of readings of implant stability in periotest (Pang et al., 2014).

Reading	Interpretation			
-8 to 0.0	Good osseointegration, the implant can be loaded.			
+0.1 to +9.9	Clinical examination is required, in most cases, loading is not possible.			
+10 to +50	Osseointegration is not sufficient, the implant cannot be loaded.			

#### Cone-beam computed tomography (CBCT):-

Cone-beam computed tomography (CBCT) is an imaging modality that offers significant advantages for the evaluation of implant patients **(Hatcher et al., 2003, Schulze et al., 2005)**. The field of view (FOV) is an important feature that describes the extent of the imaged volume from large FOV (greater than 15 cm) to medium FOV (8 to 15 cm) and limited FOV (less than 8 cm). Limited FOV units image a small area, delivering less radiation and producing a higher-resolution image **(Newman et al., 2018)**. CBCT allows for defining with elevated accuracy the quality (cortical/medullar ratio) and the quantity (height and thickness) of bone available for the implant, providing the essential information of performing or not a preimplant bony graft **(Garlaschi et al., 2014)**. when compared to medical CT, CBCT can be recommended as a dose reducing technique for dental

implant applications **(Okano et al., 2009, Qu et al., 2010)**. The effective dose from CBCT examinations ranges from 13  $\mu$  Sv with the 3D Accuitomo CBCT machine using the 4 x4 cm FOV to 479  $\mu$  Sv with the CB Mercury CBCT machine **(Table 2)**. For comparison, the effective dose from one panoramic radiograph is approximately 10 to 14 $\mu$ Sv**(Ludlow et al., 2006)**. Furthermore, the exposure from a maxillomandibular medical CT ranges from 474 to 1160  $\mu$ Sv**(Loubele et al., 2009)**. The average background radiation in the United States is 3000  $\mu$ Sv (3 mSv) per year or 8  $\mu$ Sv per day **(Table 2)**. It is important to understand that every effort must be made to reduce the effective radiation dose to the patient. By using the smallest possible FOV, the lowest mA setting, the shortest exposure time, and a pulsed exposure mode of acquisition, it is possible to accomplish effective dose reduction to the patient **(Sur et al., 2010)**.

CBCT Scanner	FOV (cm)	Effective Dose (µSv)	Digital Panoramic Equivalent (14 µSv)	No. of Days of Annual per Capita Background (3 µSv = 3000 µSv)	References
	22/13 (40 s)/13 (10 s)	82/77/48	5.9/5.5/3.4	10/9.4/5.8	Loubele et al
	6 min. (low resolution/ high resolution)	96.2/118.5	6.9/8.5	.11,7/14,4	Hatcher 
	6 max. (low resolution/ high resolution)	58.9/93.3	4.2/6.6	7.2/11	Hatcher 
	22/13	206.2/133.9	14.7/9.6	25/16	Hatcher 
	13	61.1	4.4	7,4	Silva et al p1
i-CAT next generation	23 × 17	74	5.3	9	Ludlow and Ivanovic 
	$16 \times 13$ (19 mAs)	87	6.2	10.6	Ludiow and Ivanovic 
	16 × 13 (18.5 mAs)	83	5.9	10.2	Pauwels at aP
	16 × 6	45	3.2	5.5	Pauwels et al
Newtorn 9000	23	56.2	4	6.9	Silva et al 
	12 in (male/female)	93/95	6.6/6.8	11.3/11.6	Coppenrath et al 
Vewtorn 3G	19	68	4,9	8.3	Ludiow and Ivanovic  Ivanovic 
	8 × 8 (72 mAs/96 mAs)	488/652	35/47	59/79	Ludlow and Ivanovic 
	8 × 8 (169 mAs/19.9 mAs)	122/28	8.7/2	15/1.7	Pauwels et al 
Picasso-Trio	12 × 7 (127 mAs/91 mAs)	123/81	8.8/5.8	15.1/10	Pauwels et al 
PaX-Uni3D	$5 \times 5$ max.	44	3.1	5.4	Pauwels of al 
Kodak 9000	Max. ant./min. post.	19/40	1,4/2.9	2.3/4.9	Pauwels et al 
Kodak 9500 3D	20 × 18	92			Pauwels et al 
	$15 \times 9$	136			Pauwels et al 
	20 × 18 (small/medium/ large adult)	76/98/166	5.4/7.0/11.9	9.3/12.1/20.4	Ludiow et al 
		93/163/260	6.6/11.6/18.6	11.4/20.1/32.0	Ludlow et al 
	28 mAs	84	6	10.3	Pauwels et al 
SCANORA 3D	14.5 × 13	68	4.9	8.4	Pauwels et al 
	$10 \times 7.5$	46	3.3	5.7	Pauweis et al 
Sky/View	17 × 17	87	6.2	10.7	Pauwels et al 
LUMA	19 × 19 (20 mAs/152 mAs)	96/498	7/35.6	11.9/60.6	Ludlow and Ivanovic 
	20.5 × 14 (76 mAs)	368	26.3	45.3	Pauwels et al 

# Aim and objectives:-

**Aim: -** To evaluate the osseointegration following the application of melatonin around dental implants.

### **Objectives:** -

1- Measuring primary and secondary stability of the dental implant by Periotest M device.

2- Measuring marginal bone level around the dental implant in baseline and after 6 months follow up using a cone-beam computed tomography (CBCT).

# **Research Hypothesis:-**

The topical application of melatonin powder in the osteotomy site has an effect on osseointegration around the dental implant and minimize marginal bone loss.

# Null hypothesis:-

The topical application of melatonin powder in the osteotomy site has no effect on osseointegration around the dental implants and in minimizing marginal bone loss.

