# Sample Size:

Twenty single-piece endosseous implants use for patients with at least two missing teeth in the upper or lower jaw (canine to 1st molars area).

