# **Procedure:**

Twenty single-piece endosseous implants (Dentium Co, Korea) will use to restore missing teeth in the upper or lower jaw (canine to 1st molars area) from both sides. The study will be split-mouth technique, each patient serves as his own control (served into 2 groups), the study side (topical application of melatonin in the implant side), and the control side (no melatonin in the other implant side of the same patients). According to the study reported by **(Cutando et al., 2008)** the estimated dose of melatonin required to enhance osseointegration of dental implant and minimize the marginal bone resorption is 1.2 mg of melatonin powder for each implant. CBCT for all patients before implant placement to determine bone density, dimension, and anatomical landmarks. Prior to surgery, all patients will instruct to use chlorhexidine 0.12% mouthwash as antiseptic. After local anesthesia, a mucoperiosteal flap will reflect. The manufacturer's instructions should be followed for the preparation of the implant osteotomy site. For the study

side, 1.2 mg of melatonin powder will place in the osteotomy site before the insertion of the implant. For the control side, no melatonin powder will be used and implants will be inserted directly in the prepared implant site. After dental implant installation, the gingival former will insert into the body of the fixture, then the Periotest M device will use to measure the primary stability of the DI fixture. After that, the gingival former will be removed and cover screw place and tightened into the fixture. Sutures will place after flap replacement. Patients should be instructed to use antibiotics amoxicillin 500mg and metronidazole 500mg 3 times/day for 5 days after surgical procedure, soft diet and proper oral hygiene measures. Also, CBCT immediately after implant placement to record baseline bone level, CBCT after 6 months follow up to measure marginal bone level around implant comparing with baseline measurement, and measure the secondary stability using periotest M device.

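### Do the joint research and null hypotheses leave a result on only one of the two outcomes without a conclusion?

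*Protocol*

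**What the plan says.** The Aim names one concept: "To evaluate the osseointegration following the application of melatonin around dental implants". The Objectives then list two measurements without ranking them. Item 1 is "Measuring primary and secondary stability of the dental implant by Periotest M device". Item 2 is "Measuring marginal bone level around the dental implant in baseline and after 6 months follow up", by cone-beam CT.

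The Research Hypothesis is that melatonin powder in the osteotomy site "has an effect on osseointegration around the dental implant and minimize marginal bone loss". The Null Hypothesis is that it "has no effect on osseointegration around the dental implants and in minimizing marginal bone loss".

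The Sample Size section gives only a count, "Twenty single-piece endosseous implants use for patients with at least two missing teeth", tied to neither outcome. The Procedure describes a split-mouth comparison in which "each patient serves as his own control". At six months it has the investigators compare marginal bone level with baseline and "measure the secondary stability using periotest M device". The protocol states no significance level, test or success rule.

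**The concern.** Write A for an effect on osseointegration and B for a reduction in marginal bone loss. Taken literally, the research hypothesis is A and B, and the null is neither A nor B. The cases A without B, and B without A, belong to neither statement. With no primary outcome named, one reader could call such a trial positive (the null is false) and another negative (the research hypothesis is not established).

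Two things would be at stake. The same data could support opposite headlines, with the choice made after the results are known. And if success were claimed whenever either outcome reached an unadjusted 5%, the error rate for the trial as a whole would exceed 5%.

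**Working it through.** **The wording.** Set the two hypotheses side by side, clause by clause.

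| Outcome | Research hypothesis | Null hypothesis |
|---|---|---|
| Osseointegration | an effect | no effect |
| Marginal bone loss | minimised | no effect in minimising it |

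Across the rows, the osseointegration pair is exactly complementary. The bone-loss pair is a directional alternative against its denial, so more bone loss on the melatonin side falls under the null for that outcome. On this reading each of the four combinations of A and B has a stated conclusion. Only when both rows are fused into one statement do the two mixed cases drop out. The separately numbered Objectives favour the row-by-row reading, although the protocol does not say so outright.

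**The numbers.** There is no planning calculation to reproduce: 20 implants is the only figure. Everything below is assumed: one implant per side, so 20 / 2 = 10 pairs; paired t-tests at two-sided 5%; correlation ρ between the two side differences of 0 to 0.8. Values for ρ above 0 come from simulation.

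*False positive if either outcome counts, no true effect.* At ρ = 0: 1 − 0.95² = 0.0975. At ρ = 0.5 and 0.8: about 9.2% and 8.1%. With 5 or 7 pairs the range is 8.2% to 9.8%.

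*Split result (exactly one significant), both effects real, 80% power each.* At ρ = 0: 2 × 0.80 × 0.20 = 0.32. At ρ = 0.5 and 0.8: about 24% and 15%.

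*Split result, one effect real with 80% power.* At ρ = 0: 0.80 × 0.95 + 0.20 × 0.05 = 0.77. Up to 78% at ρ = 0.8.

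*Does trial size make a split result likely?* Holding power at 80% requires an effect of 0.996 SD of the side difference at 10 pairs, 1.273 SD at 7 and 1.682 SD at 5. Because the effect is raised as the trial shrinks, these figures say nothing about size. Holding 10 pairs and varying an equal effect on both outcomes gives:

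| Effect on both (SD) | Power per test | Split result, ρ = 0.8 to 0 |
|---|---|---|
| 0.3 | 14% | 12% to 24% |
| 0.8 | 62% | 21% to 47% |
| 0.996 | 80% | 15% to 32% |
| 1.5 | 99% | about 2% to 3% |
| 2.0 | >99% | about 0% |

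With equal power p and ρ = 0 the split probability is 2p(1 − p), which cannot exceed 0.5. It is the dominant result only if melatonin affects one outcome and not the other.

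**What a written rule would buy and cost.**

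- *Both required:* joint power at ρ = 0 is 0.80 × 0.80 = 0.64, rising to about 72% at ρ = 0.8.
- *Six-month Periotest value first, bone level only if that is significant:* when both effects are real, a bone-level claim falls from 80% to the same 64% to 72%. When only bone responds, at ρ = 0 it is 0.05 × 0.80 = 0.04, and about 3.3% at ρ = 0.8.
- *Separate sentences per outcome:* no measurement, test or p-value changes.

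**The case for a change.** The best case for a change is that naming the deciding outcome belongs in the protocol itself. An unseen analysis plan would have to choose between the Aim (osseointegration only), the Objectives (two equal items) and the joint hypotheses, rather than merely add detail. The choice protects the trial only if it is made before the results are seen, and writing it down costs no patients, visits or data. The arithmetic behind the concern is also sound: the error and split-result figures were recomputed and agree within simulation noise.

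Part of this stands. No section labels a primary outcome or says what a split result means, and recording that in advance would be good practice. It does not carry the rest. A result on one outcome is not without meaning even on the strict reading, because it contradicts the null. The 8% to 10% error needs a success rule that the protocol does not contain, and handling of multiplicity is commonly left to the analysis plan. The most concrete remedy, leading with the Periotest value, is disputable: the Aim names osseointegration rather than the device, and bone level is listed as an equal objective that would lose almost all chance of a claim if it alone responded.

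**Conclusion.** No change to the plan follows. The mismatch between the hypotheses comes from reading loosely worded prose as formal joint statements; read outcome by outcome, each has its own null and alternative and nothing is left uncovered. The unwritten ranking of two outcomes is a real but modest gap, which an analyst fills sensibly by reporting both outcomes with their own conclusions and treating neither alone as proof of both.

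The possible harm is bounded: about 8% to 10% false-positive risk, and only if either outcome is counted as success without adjustment. A split result has a chance of about 15% to 32% if both effects are real at 80% power, and 77% to 78% if only one is. These figures rest on 10 pairs, paired t-tests at two-sided 5% and correlations of 0 to 0.8, none of which the protocol states. Choosing a lead outcome, or requiring both, is a trade-off on which reasonable statisticians differ, and splitting the sentences would alter no result.
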